3. STUDY OBJECTIVES AND ENDPOINTS

Primary Objective	Primary Endpoint
To assess safety and tolerability of CX-4945 administered orally BID to patients with moderate COVID-19	
Adverse events occurring from randomization (Day 1) to Day 60 (including vital signs, physical findings, clinical laboratory, and ECG results) as characterized by type, frequency, severity [(as graded by Toxicity Grading Scale for Healthy Adult and Adolescent Volunteers Enrolled in Preventive Vaccine Clinical Trials (https://www.fda.gov/media/73679/download)], timing, seriousness, and relationship to study therapy.
Secondary Objectives	Secondary Endpoints
To compare time to normalization of COVID-19-related clinical signs in CX-4945 treatment arm versus the control arm.	
Number of days from Randomization (Day1) to the day when the following clinical signs are back to normal as evaluated at every visit during the treatment period (Day 1, Day 4, Day 8, Day 11 and Day 14) and at Follow-up visits on Day 28 and Day 45 :
 
Fever is $\leq 36.6^{\circ}\text{C}$ from axillary site, or $< 37.2^{\circ}\text{C}$ from oral site or $< 37.8^{\circ}\text{C}$ from rectal or tympanic site)Respiratory rate is < 20 bpm while breathing room air at sea level$\text{SPO} \geq 96\%$ in room air without shortness of breath or dyspneaHeart rate < 90 beats per minute 
Note: If some signs listed above were caused by other conditions documented in the medical history and started before COVID-19, the patient can be considered as recovered, when these signs return to the previous (pre-COVID-19) values.

To compare duration of COVID-19-Related clinical symptoms in CX-4945 treatment arm versus the control arm.	Number of days from Randomization (Day1) to the day when: 
No key COVID-19-related symptoms scored higher than 1 as documented using a Patient Reported Outcome (PRO) instrument (a Patient Diary for Assessment of Common COVID-19-Related Symptoms – see Appendix 3),

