6.1.3. Dosing and Administration of CX-4945

Patients enrolled to the treatment Arm A will receive 1000 mg of CX-4945 BID by mouth, beginning on Day 1, and continuously through Day 14.

Patients will be instructed to take oral antiemetic prophylaxis at least 1 hour prior to taking CX-4945. Other oral medications should be taken at least one hour before or 2 hours after ingesting the dose of CX-4945 capsules.

Patients will take five 200-mg CX-4945 capsules BID, two hours after the morning meal and two hours after the evening meal (dinner) with water. Patients are advised to take 1 capsule at a time

with a pause in between each. This method may prevent a clumping effect in the stomach, so a patient is recommended to take as much as 10 minutes interval between intake of each capsule.

CX-4945 will be taken on an empty stomach with at least six ounces (180 mL) of water. After CX-4945 administration, the patient will be NPO (except for water) for 2 hours, after which, the patient may eat.

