## 1 Statistical Changes from Study Protocol

The statistical analysis methods will follow study protocol version amendment 1.0 (11-MAY-2021, exceptions and clarifications are described below:

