### 1.4.2 Method for Time to Event Data

The endpoints about time to event data as below table will be compared between treatment groups by using log-rank test, and corresponding response proportion will be presented by using Kaplan-Meier methods.

- Time to COVID-19-Related Clinical Signs Normalization
- Time to Oxygen Saturation Level Normalization
- Time to moderate COVID-19-Related Symptoms Resolution
- Time to SARS-COV-2 Viral Clearance
- Time to Improvement on NIAID 8-Point Clinical Progression Outcomes Scale (additional analysis, not mentioned in the protocol)
- Time to Improvement on EQ-5D-5L Imaginable Health Status (additional analysis, not mentioned in the protocol)

Considering the early censor on time to response (Normalization / Recovery / Viral Clearance / Improvement) data will result in over optimistic in statistical results, two data estimation methods below will be used for the sensitive analyses. Results will be claimed as robust if the results of both methods are consistent.

Time to Response (days), Best Case Scenario  
= Days to first response for responder,  
= Days to last observation for non-responder (censored)

Time to Response (days), Worst Case Scenario  
= Days to first response for responder,  
= Days to planned last observation date (31 for EQ-5D-5L and SARS-COV-2 Viral Clearance at visit 7, 45 for others at visit 8) for non-responder (censored)

Days to first response = date of first response – the first treatment date/time + 1  
Days to last observation = date of last evaluation – the first treatment date/time + 1  
For Arm SOC, the first treatment date is the date of visit 2

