## (5) Efficacy Endpoints:

- **Time to COVID-19-Related Clinical Signs Normalization: Normal when all below are met**
  - (1) Fever is <36.6°C from axillary site, or < 37.2°C from oral site, or < 37.8°C from rectal or tympanic site, or <37.2°C from forehead by using non-contact infrared thermometers
  - (2) Respiratory rate is < 20 bpm while breathing room air
  - (3) SpO2 ≥ 96% in room air without shortness of breath or dyspnea caused by COVID-19
  - (4) Heart rate < 90 beats per minute

If some signs listed above were caused by other conditions documented in the medical history and started before COVID-19, the patient can be considered as recovered, when these signs return to the previous (pre-COVID-19) values
- **Oxygen Saturation Level Normalization: Normal when SpO2 ≥ 96%**
- **Resolution of moderate COVID-19-Related Symptoms when all below are met:**
  - No key COVID-19-related symptoms scored higher than 1.
  - If some symptoms were caused by other conditions documented in the medical history and started before COVID-19 (e.g, insomnia), the patient can be considered as recovered, when these symptoms return to the previous (pre-COVID-19) value.
- **SARS-CoV-2 Viral Clearance: negative RT-PCR**

- **NIAID 8-Point Clinical Progression Outcomes Scale:**
  - 1 - Death
  - 2 - Hospitalized, on invasive mechanical ventilation or extracorporeal membrane oxygenation (ECMO)
  - 3 - Hospitalized, on non-invasive ventilation or high flow oxygen devices
  - 4 - Hospitalized, requiring supplemental oxygen
  - 5 - Hospitalized, not requiring supplemental oxygen - requiring ongoing medical care (COVID-19 related or otherwise)
  - 6 - Hospitalized, not requiring supplemental oxygen - no longer requires ongoing medical care
  - 7 - Not hospitalized, limitation on activities and/or requiring home oxygen
  - 8 - Not hospitalized, no limitations on activities
- **EQ-5D-5L Imaginable Health Status Improvement: Imaginable Health Status <90 at baseline and ≥ 90 after baseline**
- **Time to Response (Normalization / Resolution / Viral Clearance / Improvement)**

Time to Response (days), Best Case Scenario  
 = Days to first response for responder,  
 = Days to last observation for non-responder (censored)

Time to Response (days), Worst Case Scenario  
 = Days to first response for responder,  
 = Days to planned last observation date (31 for EQ-5D-5L and SARS-COV-2 Viral Clearance at visit 7, 45 for others at visit 8) for non-responder (censored)

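### The worst-case censoring day for Visit 8 endpoints (45) lies inside the visit window, so the worst case can look better than the best case; time zero and baseline responders also need clear rules

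*SAP*

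**What the plan says.** SAP 1.4.2 lists six time-to-response endpoints. They are compared by log-rank test, and the "corresponding response proportion will be presented by using Kaplan-Meier methods". Because early censoring could make results look too good, each is analysed under two scenarios that differ only for non-responders. The best case censors at the last actual observation. The worst case censors at a fixed day: "31 for EQ-5D-5L and SARS-COV-2 Viral Clearance at visit 7, 45 for others at visit 8". The SAP then states: "Results will be claimed as robust if the results of both methods are consistent". Instruction (5) repeats these rules. Instruction (4) gives the windows as 28 ± 3 for Visit 7 and 45 ± 3 for Visit 8.

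The clock is "Days to first response = date of first response – the first treatment date/time + 1", with the addition "For Arm SOC, the first treatment date is the date of visit 2". Protocol section 3 defines the signs endpoint as "Number of days from Randomization (Day1) to the day when the following clinical signs are back to normal", the same origin for both arms. Protocol 6.1.3 has CX-4945 "beginning on Day 1, and continuously through Day 14".

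On baseline status, Instruction (5) defines oxygen normalization only as SpO2 of at least 96%. EQ-5D improvement needs a baseline health score below 90, and NIAID improvement (Table 14.2.4.1) is a move from item 7 to item 8. The time-to-response layout in SAP 14.2 is headed ITT and per-protocol, with no restriction by baseline status.

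**The concern.** A worst case meant to guard against optimistic early censoring should never censor a non-responder sooner than the best case does. For the four Visit 8 endpoints (signs, SpO2, symptoms, NIAID) it can. The SAP's robustness statement rests on comparing these two scenarios, so the fault sits inside the check itself.

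Two smaller matters feed the same tables. The time origin is defined differently by arm, and for one kind of randomized patient it is undefined. Patients who already meet a response at baseline, or who cannot meet it, have no stated place in the analysis. At about 10 patients per arm, one patient is 10% of an arm.

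**Working it through.** **1. Can one rule give both fixed days?** Windows from SAP Instruction (4), stated days from SAP 1.4.2.

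| Rule | Visit 7 | Visit 8 |
|---|---|---|
| Planned day | 28 | 45 |
| End of window | 28 + 3 = 31 | 45 + 3 = 48 |
| SAP states | 31 | 45 |

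Neither rule gives both. The end-of-window rule reproduces 31, and it would give 48 for Visit 8. Three of the seven days in the Visit 8 window (46, 47, 48) lie after the stated day.

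**2. What this does to the curve.** After Day 45 the worst-case risk set holds no non-responders. If any response is dated Day 46-48, the remaining risk set consists only of responders, and the curve must end at 100%. The best-case curve stays below 100% whenever a non-responder is last seen on or after the day of the last response.

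Example, one arm of 10: seven respond by Day 28, one responds on Day 47, and two never respond and are last seen on Day 47.
- Best case: three at risk on Day 47, so response = 1 − 0.3 × (2/3) = 80%.
- Worst case, Day 45: one at risk on Day 47, so response = 1 − 0.3 × 0 = 100%.
- Worst case, Day 48: three at risk, so response = 80%.

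**3. How often.** Assumed, not in the documents: 10 per arm, exponential response times, full follow-up, response seen at the first visit (Days 4, 8, 11, 14, 28, 45) after it occurs.

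| Per arm, worst-case curve ends above best-case curve | Median 11 days | 20 | 30 |
|---|---|---|---|
| Visits spread evenly over windows | about 5-6% | about 22% | about 32% |
| Half of visits exactly on the planned day | about 2% | about 8% | about 12% |
| Day 48 in place of 45 | 0% | 0% | 0% |

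The zeros are exact for in-window visits: with Day 48 the worst-case curve ends at the simple proportion of responders, which the best-case curve cannot fall below. Replacing 45 by 48 changes log-rank significance at 0.05 in 0.1-0.4% of trials at median 11, 2-5% at 20 and 3-8% at 30 (hazard ratios 1 to 3).

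**4. Time zero.** The difference between the origins is the first-dose date minus the Visit 2 date. It is 0 for a first dose on Day 1 counted in whole dates. A first dose one day late shortens that CX-4945 patient's time by one day, and no SOC time can shift. Simulated with no drug effect, median 11 days and 0-70% of patients scored as responding on Day 1, rejection at 0.05 is 6-7% with on-time dosing and 6-9% if a quarter of CX-4945 patients start a day late. For an undosed CX-4945 patient the formula has no input. SAP Instruction (3) allows for such patients: SOC patients enter the Safety population by randomization alone, so an undosed CX-4945 patient is the only way Safety and ITT can differ.

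**5. Baseline status.** Protocol 5.1.2 excludes only SpO2 of 93% or below, so patients at 96% or more may enrol, and protocol section 3 lists Day 1 as an SpO2 assessment. Taken literally, such a patient is a response at 1 day (Day 1 − Day 1 + 1). A patient with an EQ-5D score of 90 or more, or at NIAID item 8, can never respond and would be censored. Illustration for SpO2 with half of patients normal at baseline, an assumed hazard ratio of 3 and SOC median of 11 days: power is 15-17% with Day-1 scoring and 29-30% among those at risk. With no effect, rejection is 5-8% either way.

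**The case against.** - **Day 45 is literally the planned day.** It fits the SAP's label for the fixed day, and 31 is then the outlier. This is fair as a reading of the label. But moving Visit 7 to Day 28 would make the rules agree by spreading the same fault to the Visit 7 endpoints. Only the window end serves the purpose of a worst case.
- **A visible disagreement would itself block a robustness claim.** This partly stands. A reader might infer that the fault produces false claims of robustness; the documents do not support that, since a worst case above the best case counts against consistency. The harm is that the comparison no longer means what its labels say.
- **The simulations assume full follow-up and medians chosen for illustration.** This stands. The larger percentages need medians of 20 or 30 days, and dropouts, for whom the scenarios were designed, are left out.
- **Curves ending at 100% despite a never-responder.** In the same simulations the worst-case curve does this in about 20/52/56% of arms (medians 11/20/30). A reader might take that as the size of the fault. It is not, because the best-case curve does so in about 17/32/27%.
- **Time zero is disclosed.** A reader might infer that the SAP conceals the new origin. It does not: "The statistical analysis methods will follow study protocol version amendment 1.0" is followed by a notice that exceptions and clarifications come next, and 1.4.2 is one of them. What is missing is a flag that the origin departs from the protocol. Nor do the documents support a claim of bias towards CX-4945, because randomization, Visit 2 and first dose are all planned for Day 1.
- **Normalization and improvement imply an abnormal start, and the layout has a row for missing values.** This stands to the extent that the SAP nowhere says baseline-normal patients are kept. Their inclusion is an inference from the ITT/per-protocol heading and the absence of an exclusion rule. The signs and symptoms endpoints are largely protected by the entry criteria (respiratory rate at least 20 or heart rate at least 90; two symptoms scored 2 or more).

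**Conclusion.** The censoring mismatch is certain: no single rule gives 31 and 45, and for Visit 8 endpoints the worst case can censor before the best case. Its effect is on the curves and the best/worst comparison, and depends on visits falling on Days 46-48. It rarely changes a p-value, and nothing here shows that the log-rank results are invalid.

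The arm-specific origin is a real gap in definition. It has no numerical effect when first doses are on Day 1 and whole dates are used; what remains is the undosed ITT patient and the undefined use of clock time. The baseline question is one of unspecified handling. If such patients are kept, it dilutes the comparison and, on a common clock, causes no bias on average.

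Severity is minor. All the endpoints concerned are secondary or added by the SAP, the study has about 20 patients with no power calculation (protocol 9.3), and its primary endpoint is safety.

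**What to change.** In SAP 1.4.2 and Instruction (5):

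1. Set the worst-case censoring day for Visit 8 endpoints to 48, the window end, matching 31 = 28 + 3.
2. Use the randomization/Visit 2 date as time zero in both arms, whole dates only. This restores the protocol's origin and gives every ITT patient a time zero.
3. For SpO2, EQ-5D and NIAID, add an analysis of patients who do not already meet the response at baseline and are able to meet it. Count only post-baseline responses and show the number excluded by arm. Keep the all-ITT result beside it, since protocol 9.7.1.1 makes ITT the primary population for secondary efficacy endpoints, and state how baseline responders are scored there.

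Items 1 and 2 cost SAP wording and programming and lose no patients. Item 3 gives a small subset of unknown size: about 7, 5 or 3 per arm if 30%, 50% or 70% are excluded. At 70%, a given arm has a 15% chance of one or no at-risk patient (0.7^10 + 10 × 0.3 × 0.7^9 = 0.149); at 50% the chance is 1%. These tests stay weak, which is a further reason to report both analyses.

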### 1.4.3 Method for Continuous Data

Demographics, baseline characteristics and continuous efficacy data will be analyzed by using two sample t test or Wilcoxon rank-sum test as appropriate. Net changes from pre-treatment laboratory test results and vital signs will be analyzed by using ANCOVA model with baseline value as covariate or Wilcoxon rank-sum test as appropriate.

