
● To evaluate other Clinical Benefit of treatment with CX-4945 relative to the control arm	
● All-cause mortality status – the number of deaths occurred in each treatment group from Randomization (Day 1) through Day 60.● Number of patients hospitalized in each treatment group from Randomization (Day 1) to Day 45● Number of days to normalization of oxygen saturation level measured by pulse oximeter at Randomization (Day 1), Day 4, Day 8, Day 11, Day 14, Day 28 and Day 45 and categorized as <96% versus ≥96%.● Proportion of patients with disease progression or improvement in health status occurring from Randomization (Day 1) to Day 28. Disease progression is defined as change in patient health status assessment from item 7 to items 1- 6 and health improvement -as change from item 7 to item 8, evaluated by the ordinal NIAID 8- point Clinical Progression Outcomes scale – collected at every visit. from randomization (Day 1) through Day 45. An 8-category ordinal scale of patient health status ranges from:
1. Death;2. Hospitalized, on invasive mechanical ventilation or extracorporeal membrane oxygenation (ECMO);3. Hospitalized, on non-invasive ventilation or high flow oxygen devices;4. Hospitalized, requiring supplemental oxygen;5. Hospitalized, not requiring supplemental oxygen - requiring ongoing medical care (COVID-19 related or otherwise);

	
6. Hospitalized, not requiring supplemental oxygen - no longer requires ongoing medical care;7. Not hospitalized, limitation on activities and/or requiring home oxygen;8. Not hospitalized, no limitations on activities. 
• Changes in EQ-D5-5L (used as an indicator of symptom improvement) from Baseline (Day 1) to Day 8, 14, 28.

• To evaluate changes in inflammatory markers	
• Changes in plasma IL-6 level from Randomization (Day 1) to Day 4, Day 8, Day 11, and Day 14.• Changes in CRP, LDH, CPK, ferritin, D-dimer from randomization (Day 1) to Day 4, Day 8, Day 11, and Day 14.

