8.1. STUDY PROCEDURES

8.1.1. Screening Period:

The patient will sign and date the informed consent form (ICF) and Health Insurance Portability Accountability Act (HIPAA) authorization (according to site policy and practices) prior to any study-related procedures. The study center will maintain the study-specific screening and enrollment logs at their site.

For screening procedures see the Schedule of Activities in **Section 1.3** and Assessments in **Section 8.2**.

8.1.2. Treatment Period:

For the treatment period procedures see the Schedule of Activities in **Section 1.3** and Assessments in **Section 8.2**.

Patients who meet the eligibility criteria and are randomized will have completed the following evaluations and assessments on Day 1 prior to treatment: review of any changes in medication history, physical examination, vital signs, clinical status – ordinal scale assessment and COVID-19-related symptoms scale assessment, EQ-D5-5L questionnaire, pulse oxygen saturation (SpO₂), Nasopharyngeal Swab Sample Collection (for quantitative virologic testing viaRT-PCR), laboratory sample collection for routine serum biochemical, hematologic, coagulation, IL-6 levels and CRP, LDH, CPK, ferritin, D-dimer analysis.

During the treatment phase, patients randomized to the treatment arm A will receive CX-4945 (1000 mg) twice a day for up to 14 days. Details on CX-4945 administration can be found in **Section 6**.

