9.3. SAMPLE SIZE DETERMINATION AND RATIONALE

A total of approximately 20 subjects will be randomized 1:1 in this study. The sample size is based on clinical judgment. No statistical power calculation is used to establish the sample size for this proof-of-concept study.

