9.7.2. Covariates

For efficacy analyses important prognostic factors that need adjustment will be specified in the SAP for the study

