## 14.2.5 EQ-5D-5L

### 14.2.5.1 EQ-5D-5L

Population: Intent-to-Treat Population / Per-Protocol Population

Characteristics	Treatment Group	Difference	P-value
--Repeat Population: <See populations above>			

. Repeat Visit:

Visit 2 (Day 1), Visit 4 (Day 8), Visit 6 (Day 14, EOT), Visit 7 (Day 28, F1), LOCF

. Repeat Variable:

*Total score of Q1~Q5, Imaginable Health Status*

N (Missing)	XXX (XXX)	TW (Visit 2 (Day 1)) 0.XXXX
Mean (SD)	XXX (XXX)	
Median (IQR)	XXX (XXX)	
Q1~Q3	XXX~XXX	
Min~Max	XXX~XXX	

*For Imaginable Health Status only*

≥ 90	XXX (XXX.X%)
< 90	XXX (XXX.X%)

Repeat [Visit - Visit 2 (Day 1)] except Visit 2 (Day 1)

N (Missing)	XXX (XXX)	TW 0.XXXX
N (Missing)	XXX (XXX)	
Mean (SD)	XXX (XXX)	
Median (IQR)	XXX (XXX)	
Q1~Q3	XXX~XXX	
Min~Max	XXX~XXX	

For W, normality is not applied

Groups Diff	§C - §S
Median (Asymptotic SE)	XXX
95% CI (HL)	XXX~XXX

For T, normality is applied

Groups Diff	§C - §S
Mean (SD)	XXX (XXX)
95% CI	XXX~XXX

Q1. Mobility, Q2. Self-Care, Q3. Usual Activities, Q4. Pain/Discomfort, Q5. Anxiety/Depression

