### 14.3.6 Laboratory Examination – Urinalysis

- 14.3.6.1 Urinalysis – <Item 1 and Unit>
- 14.3.6.2 Urinalysis – <Item 2 and Unit>
- 14.3.6.3 .... Refer to [Instructions and Abbreviations] of section 16 for the test terms

*<LB Layout 1: For Continuous Laboratory Test; Clinical relevance analyses will be excluded if not applicable>*

Population: Safety Population

Characteristics	Treatment Group	Difference	p-value
. Repeat Visit: No ‘Visit 1 (Screening)’ for IL-6: Visit 1 (Screening), Baseline, Adjusted Visit 3 (Day 4), Adjusted Visit 4 (Day 8), Adjusted Visit 5 (Day 11), Adjusted Visit 6 (Day 14, EOT), Visit 7 (Day 28, F1), Visit 8 (Day 45, F2)			
N (Missing)	XXX (XXX)		
Mean (SD)	XXX (XXX)		
Median (IQR)	XXX (XXX)		
Q1~Q3	XXX~XXX		
Min~Max	XXX~XXX		
		T/W <Baseline Only>	
		0.XXXX	

For W, normality is not applied <Baseline Only>

Groups Diff	§C - §S
Median (Asymptotic SE)	XXX
95% CI (HL)	XXX~XXX

Characteristics	Treatment Group	Difference	p-value
For T, normality is applied <Baseline Only>			
Groups Diff		§C - §S	
Mean (SD)		XXX (XXX)	
95% CI		XXX~XXX	
N (Missing)	XXX (XXX)		
Normal	XXX (XX.X%)		
NCS	XXX (XX.X%)		
CS (Medical History)	XXX (XX.X%)		
CS (Adverse Event)	XXX (XX.X%)		
. Repeat [Visit – Baseline] excluding Visit 1 (Screening) and Baseline			ANCOVA/W
N (Missing)	XXX (XXX)		0.XXXX
Mean (SD)	XXX (XXX)		
Median (IQR)	XXX (XXX)		
Q1~Q3	XXX~XXX		
Min~Max	XXX~XXX		
95% CI (WI)	XXX~XXXwt		
For W, normality is not applied			
Groups Diff		§C - §S	
95% CI (HL)		XXX~XXX	
For ANOVA, normality is applied	XXX (XXX)		
LsMean (SE)	XXX~XXX		
95% CI of LsMean			
Groups Diff. (T)		§C-§S	
Difference of LsMean		XXX	
95% CI of LsMean		XXX~XXX	
ANCOVA Model (p-value 0.XXXX) with effect Treatment (p-value 0.XXXX), Baseline (p-value 0.XXXX), Treatment*Baseline (p-value 0.XXXX).			
. Repeat [<Baseline> to <Visit>]			
N (Missing)	XXX (XXX)		
Relieved	XXX (XX.X%)		
Unchanged	XXX (XX.X%)		
Worsened (Medical History)	XXX (XX.X%)		
Worsened (Adverse Event)	XXX (XX.X%)		

For Item excluding IL-6 Baseline is Visit 2 (Day 1) data, or is Visit 1 if Visit 2 (Day 1) is null

For IL-6 Baseline is Visit 2 (Day 1) data

Refer to [Instructions and Abbreviations] of title pages for Transition of Clinical Relevance

**<LB Layout 2: For Categorical Urinalysis Test, including pH;  
 MHCHISQ for PH, C/F for else>**

Population: Safety Population

Characteristics	Treatment Group	p-value

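### EQ-5D-5L change from Day 1 is compared between arms without the Day 1 score as a covariate; the planned test is valid but at low to moderate correlation gives up precision that ANCOVA would recover

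*SAP*

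**What the plan says.** Protocol section 3 lists as a secondary endpoint: "Changes in EQ-D5-5L (used as an indicator of symptom improvement) from Baseline (Day 1) to Day 8, 14, 28". Protocol 8.1.2 places the questionnaire among the Day 1 assessments completed before treatment: "COVID-19-related symptoms scale assessment, EQ-D5-5L questionnaire, pulse oxygen saturation". The baseline value should therefore exist for nearly every randomized patient.

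SAP 1.4.3 divides continuous variables into two groups. For the first: "Demographics, baseline characteristics and continuous efficacy data will be analyzed by using two sample t test or Wilcoxon rank-sum test as appropriate". For the second: "Net changes from pre-treatment laboratory test results and vital signs will be analyzed by using ANCOVA model with baseline value as covariate", again with Wilcoxon as the alternative.

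The mock tables carry the division through. In Table 14.2.5.1 the change rows, "Repeat [Visit - Visit 2 (Day 1)] except Visit 2 (Day 1"), are labelled for t test or Wilcoxon and have no LS-mean or covariate row. In the continuous laboratory layout the change rows, "Repeat [Visit – Baseline] excluding Visit 1 (Screening) and Baseline", are labelled ANCOVA or Wilcoxon, with LS-means and a model footnote. The vital-signs table (14.3.8) does the same. No other section adds a baseline-adjusted EQ-5D-5L analysis.

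On covariates, Protocol 9.7.2 says: "For efficacy analyses important prognostic factors that need adjustment will be specified in the SAP for the study". The SAP names none for EQ-5D-5L.

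**The concern.** The protocol planned no inferential statistics. SAP 1.4.1 adds between-arm testing, and Table 14.2.5.1 attaches p-values and 95% intervals to EQ-5D-5L change. Once a comparison is to be made, it should use the baseline information already in hand, especially with so few patients.

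Two things are lost by not doing so. The interval is wider than it need be unless the baseline-to-visit correlation is high. Also, subtracting the Day 1 score in full over-corrects for a chance imbalance whenever the correlation is below 1, so the arm that happens to start worse appears to improve more. With about 10 patients per arm, sizeable chance imbalances are common.

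**Working it through.** **Inputs from the documents.** Protocol 9.3: "A total of approximately 20 subjects will be randomized 1:1 in this study", so about n = 10 per arm and N = 20. No SD, effect size, power or baseline-to-visit correlation is stated, so there is no figure of the plan's own to reproduce.

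**Assumptions.** Equal variance at Day 1 and at the visit; normal data; two-sided 0.05 (the mock table gives 95% intervals); correlation ρ from 0.2 to 0.9.

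**Variance.** In units of the common variance, a change score has variance 2(1 − ρ) per patient. ANCOVA leaves residual variance 1 − ρ². The large-sample ratio is (1 − ρ²) / [2(1 − ρ)] = (1 + ρ)/2. Estimating the slope from 20 patients costs a factor (N − 3)/(N − 4) = 17/16. The interval-width ratio is the square root of the product, times the ratio of the t quantiles on 17 and 18 degrees of freedom. The matching n is 10 divided by the adjusted ratio.

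| ρ | (1+ρ)/2 | × 17/16 | CI width ratio, formula | CI width ratio, simulated | n per arm for change score to match ANCOVA with 10 |
|---|---|---|---|---|---|
| 0.2 | 0.60 | 0.64 | 0.80 | 0.80 | 15.7 |
| 0.3 | 0.65 | 0.69 | 0.83 | 0.83 | 14.5 |
| 0.5 | 0.75 | 0.80 | 0.90 | 0.89 | 12.5 |
| 0.7 | 0.85 | 0.90 | 0.95 | 0.95 | 11.1 |
| 0.9 | 0.95 | 1.01 | 1.01 | 1.01 | 9.9 |

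**Simulation** (20,000 trials per setting, 10 per arm, t test on change against ANCOVA). Type I error was about 5% for both methods. For an illustrative true difference of 1 SD, power went from 39% to 56% at ρ = 0.2, 44% to 58% at 0.3, 56% to 66% at 0.5 and 78% to 82% at 0.7, with no gain at 0.9.

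**Chance imbalance.** The difference in Day 1 means has SD √(2/10) = 0.447 of a baseline SD. The chance that it exceeds 0.25, 0.5 or 0.75 SD in either direction is 58%, 26% and 9%. Given a realised difference d, the change-score estimate is shifted by (ρ − 1)d. For d = 0.5 SD this is −0.40, −0.35, −0.25, −0.15 and −0.05 SD at ρ = 0.2, 0.3, 0.5, 0.7 and 0.9. ANCOVA removes this term, apart from the error in estimating the slope.

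**The case against.** The strongest reply is that the planned comparison is sound. It already subtracts the Day 1 score and holds its type I error. A reader might infer that it is biased. It is not: the shift (ρ − 1)d averages to zero over randomizations and is an error only conditional on the imbalance that occurs. This stands, and it makes the point one of efficiency.

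The gain also depends on a correlation the documents do not give. At 0.7 it is about 10% of the variance, and at 0.9 it has gone. This stands too, and is why the full range is shown.

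A reader might infer that the SAP keeps its better method for safety data. The documents do not support that. CRP, LDH, CPK, ferritin, D-dimer and IL-6 changes are a secondary objective in Protocol section 3, and SAP 14.3.4 reports inflammatory markers among the laboratory tables that use ANCOVA. Under SAP 3.1 the laboratory and vital-sign analyses also fall back to an unadjusted Wilcoxon test when Shapiro-Wilk gives p ≤ 0.05.

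A reader might also infer that the SAP breaches Protocol 9.7.2. That sentence covers factors that need adjustment; it neither requires that there be any nor mentions the EQ-5D-5L baseline. Silence in the SAP is an omission worth filling, not a contradiction.

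Finally, the calculation covers the t test against ANCOVA. It does not model the Shapiro-Wilk switch, Wilcoxon or rank ANCOVA, although a five-item sum and a bounded 0-100 scale may well trigger the switch. The figures are therefore a guide to size, not a prediction for the procedure as a whole.

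**Conclusion.** The point holds as one of precision. EQ-5D-5L change is to be compared without the Day 1 score as covariate, although that score is collected and the SAP already uses baseline adjustment elsewhere. At correlations of 0.2 to 0.5, ANCOVA would cut the variance by roughly 36% to 20%; at 0.7 by about 10%; at 0.9 it would cost about 1%. These figures rest on 10 per arm, equal variances, normal data and an assumed correlation. The possible loss is negligible over this range and the possible gain is worthwhile.

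The documents do not support calling the planned test invalid or biased over repeated randomization. Nor does the point bear on the primary conclusion: the primary endpoint is safety, EQ-5D-5L is one of several measures under other clinical benefit, and the sample size was set by clinical judgment without a power calculation. Priority is modest.

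**What to change.** In SAP 1.4.3 and Table 14.2.5.1:

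- Make ANCOVA on treatment and the Day 1 value the analysis for both the total score and the 0-100 health status at each post-baseline visit. Using the visit value or the change as the response gives the same treatment estimate.
- Fit main effects only. The laboratory and vital-sign footnotes list a treatment-by-baseline term, which should not be copied across.
- Report the adjusted difference with its 95% interval.
- If the normality rule in SAP 3.1 triggers, use rank ANCOVA instead of an unadjusted Wilcoxon test, so that the adjustment is not dropped.
- Keep the t/Wilcoxon result as a sensitivity analysis.

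Make the same change for viral-load change in Table 14.2.3.1, which has the same t/Wilcoxon test on change, using the baseline that table already defines.

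The cost is one degree of freedom, a few lines of SAP text and small programming changes. The laboratory model cannot be reused exactly, because of its interaction term and its unadjusted fallback. No new data are needed.
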